The KPC surveys will be implemented in the 24 priority countries where the USAID-funded MCSP will have a presence as well as other countries where in-country USAID missions buy into MCSP to conduct these studies. This generic protocol will have JHSPH (Johns Hopkins Bloomberg School of Public Health) as the IRB of record; the MCSP consortium partner IRBs (JSI [John Snow International], PATH, PSI [Population Services International]) will receive the final approved version. Country-specific plans detailing the sampling and procedures will be added to this generic protocol as "annexes"; this will be done through submitting amendments of the generic protocol to JHSPH's IRB, reflecting any relevant changes that will be made in order to maintain the annexes added as subsets of the generic protocol.

The KPC is a flexible survey tool that can be tailored for various technical areas and combination of areas while maintaining standards for collection of information for specific interventions. For example, all programs that include control of diarrheal disease will collect information about the percentage of children who had diarrhea in the two weeks preceding the survey, were given oral rehydration solution (ORS), and were given zinc. However, programs that do not focus on diarrhea will not collect information on treatment of diarrhea.

KPC surveys will be repeated at various times during MCSP program implementation in a target country, from annually to every 2–3 years. In most cases surveys will be implemented only in MCSP intervention areas, but if the opportunity exists surveys may also be carried out in comparison areas. Specific details for each country conducting a KPC survey will be added as an annex to this generic protocol.

Justification of Sample Size

In order for the KPC to be adapted to what is needed for specific studies, the design provides for limited choices regarding sampling methodology, household selection, respondent selection, and sample size. Each study amendment will specify which options were chosen to be implemented in the individual study.

Sampling Methodologies

The following are the three options for sampling methodology, each of which can be implemented with or without parallel sampling. All sampling methodologies will include a step of choosing clusters.

- 1. 30-cluster, with number of interviews conducted per cluster varying from 7-30
 - a. Parallel sampling
 - b. Without parallel sampling

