- 2. LQAS (lot quality assurance sampling), minimum of 19 interviews per supervision area, minimum of 5 supervision areas
 - a. Parallel sampling
 - b. Without parallel sampling
- 3. Stratified random sampling
 - a. Parallel sampling
 - b. Without parallel sampling

Choosing Clusters

Clusters will be determined by probability proportion to size (PPS). The definition of a cluster may vary country to country. In most cases clusters will be communities in rural areas and neighborhoods in urban areas; however, alternative divisions of populations may be used if appropriate to the country setting. The following are the steps for PPS:

- 1. Create a list (ordered randomly) of communities (or other appropriate division), the population for each, and the total population of all communities (estimates are fine).
- 2. Calculate the cumulative population of each community by summing the total population of the community with the combined total population of all the preceding communities on the list.
- 3. Determine the sampling interval by dividing the total population of the entire program area by the total number of clusters, which is 30 for a 30-cluster survey, a minimum of 95 for LQAS, and a minimum of 96 for stratified.
- 4. Choose a random number to identify the starting point on the list to begin selecting clusters. The random number must be less than or equal to the sampling interval.
- 5. Beginning with the random number, use the sampling interval to identify communities for the clusters (30, 96, or 95).

Household Selection (within a Cluster)

The following are options for household selection.

- 1. In the field, at the time of conducting interviews
 - a. "Spin the bottle"
 - b. Mapping
- 2. With a pre-existing list

In all cases larger clusters should be subdivided before beginning household selection. For urban areas in particular, selection rules must be developed ahead of time on how to handle different housing types, such as high rises or multiple families living in a single dwelling. "Spin the bottle" and mapping are applied at the time of data collection, while using a pre-existing list involves household selection before beginning data collection in the field. For "spin the bottle," the interview team selects the center of the cluster and spins the bottle to determine which direction to go for interviews. Households are selected based on a set (*k*th) interval of households from the center or the nearest neighbor's door.

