For studies that interview women and/or men ages 15–17 years, consent will be obtained from an adult in the household to conduct the interviews or, in the case of emancipated minors (according to local legal definition), they will give their own consent.

Households within each sampled cluster will be visited by the data collectors. Interviewers will ask to speak to an adult (18 years of age or whatever the local legal age of majority is), and if available the interviewers will ask screening questions (and fill out a screening form) to determine whether an eligible mother or father is present in the household. The screening form will be destroyed at the end of the fieldwork. If the answer is yes, and he or she is home and he or she agrees to participate following an informed consent/assent process, then he or she is interviewed. If he or she is not home but expected back within 30 minutes, the interview team will return to the house no more than three times before finishing all the interviews in the area. If unavailable, he or she will be counted as "Non-response" and substituted with someone from another household.

When no eligible mother or father is available in a household, then the interview team proceeds to the next house selected to be visited. If a mother has more than one child age 0–59 months, normally they will be asked about the youngest child. However, for some countries, it can be predetermined to select one of the mother's children at random.

Sample Size Determination

Specific sample sizes will vary from country to country. However, sample sizes will be calculated to provide estimates with confidence levels of 95 percent and precision of 10 percent for key indicators. For stratified random sampling and LQAS the design effect is 1. For 30-cluster sampling a design effect of 2 will be assumed. For all cases, if indicators are to be disaggregated, the total sample size must be multiplied by the number of disaggregation categories; if parallel sampling is needed the sample size must be increased to ensure adequate sample sizes for all indicators collected. Final sample sizes will be powered on the most important indicators, which may result in wider confidence intervals for a few of the other indicators.

For individual studies, decisions will be made regarding the most important indicators for which to collect information. The sample size will be powered for these indicators. After this the study will use the

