- 3. Each individual respondent will be asked to spend about 60–75 minutes with the interview team, including introductions, description of privacy measures, consenting, and responding to interview questions. Respondents will *not* be followed up for additional information. The majority of the studies will be cross-sectional of 1–4 months' duration per each data collection period.
- 4. The interview team will provide a brief data analysis plan and a description of variables to be derived. Each survey module contains indicator definitions and tabulation plans. Analysis will generally focus on generating frequencies and occasionally on cross-tabulations. (See modules for details.) For example, the on the data tabulation plans for selected key maternal indicators is based on data collected through the Maternal and Newborn Care Module. Any statistical software or hand tabulation procedure may be used as long as standardized tabulation plans are followed. In addition, for LQAS, decision rule tables will be used to assess whether or not a supervision area has reached expected results. However, care will be taken not to prematurely remove resources from any supervision area

Illustrative Key Maternal Health Indicators		
Indicator 1.2	Antenatal Care (4+ visits)	
Indicator 1.13	IPT _P (3+)	
Indicator 1.14	LLIN Use	
Indicator 2.1	Skilled Attendant at Birth	
Indicator 2.2	Facility Birth	

The following are examples of indicators and tabulation plans from the MNC module.

Data Tabulation Plans ¹⁰			
I.2, 6.2 Antenatal Care (4+) Percentage of mothers of children ages 0– 23 months who had four or more antenatal visits while pregnant with their youngest child	Number of mothers of children ages 0–23 months who had four or more antenatal visits while pregnant with their youngest child 4 ≤ MN105 < 98		
	Total number of mothers of children ages 0–23 months in the survey	× 100	

¹⁰These tabulation plans and indicators are examples from one of the current modules (Maternal and Newborn care). Target populations (denominators) for these indicators may vary, depending on the specific survey. Variations will be explained in amendments submitted for specific surveys.

Data Tabulation Plans ¹⁰			

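### For lot quality assurance sampling (LQAS), the one cluster draw over the whole program area is practically certain, at 95 draws, not to give every supervision area its required 19 interviews

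*Protocol*

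**What the plan says.** All points are in the Protocol.

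- **Section 3, Sampling Methodologies.** The LQAS option is set at a "minimum of 19 interviews per supervision area, minimum of 5 supervision areas". The lead-in to the three options states: "All sampling methodologies will include a step of choosing clusters".
- **Section 3, Choosing Clusters.** One five-step procedure, with probability proportional to size (PPS), serves all three options. Step 1: "Create a list (ordered randomly) of communities (or other appropriate division), the population for each". Step 3: "Determine the sampling interval by dividing the total population of the entire program area by the total number of clusters", with the number of clusters given as 30 for the 30-cluster design, "a minimum of 95 for LQAS, and a minimum of 96 for stratified". Steps 4 and 5 take one random start and step through the list. Supervision areas are not mentioned in any step.
- **Section 3, Sample Size Determination.** "For stratified random sampling and LQAS the design effect is 1".
- **Section 4, Study Implementation, item 4.** For LQAS, "decision rule tables will be used to assess whether or not a supervision area has reached expected results".

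**The concern.** The LQAS requirement is set area by area, but the draw is made for the program area as a whole. Under a whole-area PPS draw, a supervision area receives clusters in proportion to its population, with chance variation on top because the list is in random order. Nothing holds the count at 19.

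Classifying each supervision area is what sets LQAS apart from the other two options. If an area ends with 8 or 10 interviews, its classification carries much larger errors than at 19, and small areas fare worst. Because this is a generic protocol, any country annex that chooses LQAS and follows the steps inherits the problem.

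**Working it through.** **Inputs from the protocol.** At least 19 interviews per supervision area; at least 5 areas; at least 95 clusters for LQAS; one randomly ordered list; interval = total program-area population / number of clusters; design effect 1 for LQAS; 10-point precision.

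**Inputs assumed.** One interview per LQAS cluster (not stated; inferred in step 1). Population shares of the areas: equal, 30/25/20/15/10%, or 40/25/15/12/8%. Coverage thresholds of 80% and 50%, for illustration.

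**1. The protocol's own figure.** 5 areas × 19 interviews = 95. The match is exact and implies one interview per cluster. The number is right; the question is how the 95 are drawn.

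**2. Expected interviews per area.** Expected n = 95 × w.

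| Assumed shares | Expected interviews |
|---|---|
| 20/20/20/20/20% | 19 in each |
| 30/25/20/15/10% | 28.5, 23.75, 19, 14.25, 9.5 |
| 40/25/15/12/8% | 38, 23.75, 14.25, 11.4, 7.6 |

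**3. Chance that all five areas reach 19 at 95 draws.** With 95 draws and five areas, all can reach 19 only if each gets exactly 19. For equal areas, treating the draws as multinomial:

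95! / [(19!)^5 × 5^95] = 0.00015.

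Simulating the five steps as written, with communities of unequal size, agrees. The chance was 0.00025 with 500 communities (4,000 runs), 0.001 with 200, and 0 with 2,000. With 500 communities the smallest area had a median of 15 interviews (5th to 95th percentile 12 to 17). With shares 30/25/20/15/10%, no run in 4,000 met the minimum everywhere, and the smallest area had a median of 9 (5 to 13).

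**4. Draws needed if the whole-area draw were kept.** For equal areas, the chance that all reach 19 was 0.949 at 140 draws and 0.981 at 150 in simulation with 1,000 communities. The multinomial calculation gives 0.908 and 0.966. So about 150 draws are needed for roughly 95%. With shares 30/25/20/15/10%, the simulated chance was 0.931 at 240 draws and 0.96 at 260.

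**5. Effect on classification.** An area passes if at least d respondents are covered. The errors are P(X < d | 80%) and P(X ≥ d | 50%), with X binomial.

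- n = 19, d = 13: 6.8% and 8.4%.
- n = 8, d = 6 (the cut-off with the smallest maximum error): 20.3% and 14.5%.
- n = 10, d = 7: 12.1% and 17.2%.

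**6. What drawing 19 within each area does to the pooled estimate.** The sample is no longer self-weighting, so the pooled estimate is Σ w·p, with variance Σ w²·p(1 − p)/19.

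- Every area at 50% coverage: half-width = 1.96 × √(0.25 × Σw² / 19). With shares 30/25/20/15/10%, Σw² = 0.225 and the half-width is 10.7 points. With 40/25/15/12/8%, Σw² = 0.2658 and it is 11.6 points. With equal areas, Σw² = 0.20 and it is 10.05 points.
- Coverage of 80/70/50/40/30% from largest to smallest area: 9.5 points with the first set of unequal shares and 9.97 with the second.

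**The case against.** The strongest reply is that this is a generic protocol. Country plans with the sampling details are added as annexes and reviewed as amendments, and LQAS is one option of three. That is a real checkpoint, but it does not cure the text. Section 3 describes limited choices, with each amendment stating which were taken, and it offers no alternative way to choose clusters.

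Several further objections stand, and they limit the point:

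- **95 is a minimum.** A reader might infer that the procedure can never deliver 19 per area. The documents do not support that, since a larger draw is allowed and would usually succeed. What holds is near-certain failure at 95.
- **Clusters and interviews are different units.** One interview per LQAS cluster is an inference, and more per cluster would change the counts.
- **The stratified option.** A reader might infer the same flaw there, because strata do not enter the draw either. But the protocol sets no minimum and no decision rule per stratum, so no stated requirement is broken.
- **The pooled estimate.** A whole-area PPS draw is approximately self-weighting, so it remains valid for the program area. Bias would arise only if teams took 19 per area and pooled without weights, and the protocol prescribes neither.
- **The design effect.** It is tempting to replace 1 by k × Σw² for k equally sampled areas. That formula assumes equal variances and ignores the gain from stratifying, so it overstates the loss when coverage differs between areas (step 6 of the working).
- **The decision rules.** The protocol does not say that the tables are read at n = 19 whatever number was achieved, and it urges caution before resources are withdrawn from an area. This softens the consequence, but a table matched to n = 8 still has the larger errors.

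**Conclusion.** The point holds for the LQAS option. The cluster-selection steps, as written, do not secure the protocol's own minimum of 19 interviews per supervision area, on which the area-level decision rules rest. At 95 draws with one interview per cluster, the minimum is practically certain to be missed in at least one area: the chance of meeting it everywhere is about 0.00015 with five equal areas, the case most favourable to the protocol, and smaller with unequal ones. That result needs no assumption about unequal shares. It does rest on one interview per cluster and on drawing the stated minimum of 95. The size of the shortfall in a given area, and the rise in error to about 20% and 14% at n = 8, depend on assumed shares and thresholds.

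**What to change.** In Choosing Clusters, add for LQAS that steps 1 to 5 are run separately within each supervision area: a list of that area's communities, an interval equal to that area's population divided by its number of draws (at least 19), and its own random start. State the number of interviews per LQAS cluster. With one interview per cluster, every area then gets at least 19 by construction, and the minimum total stays at 5 × 19 = 95.

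Add that estimates pooled to the program area weight each supervision area by its population share. In Sample Size Determination, qualify the design effect of 1 for the pooled LQAS estimate, without substituting k × Σw². It is enough to say that precision may be slightly worse than 10 points when areas differ in size.

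The cost is rewording and no extra interviews. The price in precision is a pooled half-width of at most about 10.7 to 11.6 points under the two assumed sets of unequal shares if every area is at 50% coverage, and near 10 points or better when coverage differs strongly between areas. Keeping the whole-area draw would instead need about 150 draws with five equal areas, and about 260 with shares of 30/25/20/15/10%. The change should be made before any country annex uses LQAS.

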appropriate sample size formula based on the chosen sampling methodology. The value of p (proportion) should be .5 (50%) given that these surveys collect information from a variety of indicators with varying proportions in a population, many of which may not be known before the survey is implemented. A p value of .5 gives the maximum sample size needed to estimate any level.

The sample size for a single survey designed to estimate levels at one point in time (not compared with another group) will be determined by the following:

For stratified sampling, simple random sampling, and LQAS:

$$N = Z\alpha^2 pq / d^2$$

- $Z\alpha = 1.96$ corresponding to a confidence level of 95%
- p = 0.5 (maximum sample size)
- q = 1 0.5 = 0.5
- d =accuracy desired = 10% = 0.10
- $N = (1.96)^2 \times 0.5 \times 0.5 / (0.10)^2 = 96$

For 30-cluster sampling, samples size collected from the preceding formula will be multiplied by 2:

$$N_C = N \times \text{deff}$$

Thus, $N_C = 192$

The number of households visited will be calculated based on estimates of the percentage of families expected to have children in the needed age groups. For example, if it is estimated that 45 percent of households have children 0–23 months and 166 eligible mothers must be interviewed, then survey teams may have to visit N_1 =166 × (100 / 45) = 369 households.

Sample sizes for comparison of two phases or groups will use the following formula for stratified random sampling or simple random sampling:

$$N_1 = N_2 = [Z\alpha_{1/2} + Z\beta]^2 [2pq] / (p1 - p2)^2 = [1.96 + 1.28]^2 [2(.5)(.5)] / (.2)^2 = 1.31$$

- N_1 = baseline sample size
- N_2 = final evaluation sample size
- $Z\alpha_{/2}$ is the Z value corresponding to the chosen level of risk α . ($Z\alpha_{/2}$ should be used in two-sided tests, and $Z\alpha$ should be used in one-sided tests.)
- $Z\beta$ is the Z value corresponding to the chosen level of risk β (it directly relates to the "power" of the test as power = 1β ; ($Z\beta$ = 1.28 for a power of .9)
- p_1 is the expected coverage at baseline (can be set to .5 for maximum sample size)

•
$$q_1 = 1 - p_1$$

• p_2 is the expected final coverage (can be set to .5 for maximum sample size)

•
$$q_2 = 1 - p_2$$

- $p = (N_1 p_1 + N_2 p_2) / (N_1 + N_2)$
- q = 1 p

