Before beginning field work, the research team will contact national and regional or county level authorities in writing, describing the study and seeking permission to carry out the KPC survey. The relevant authorities will communicate to the community leaders about the study through their usual channels such as letters introducing the research team to them. Next the research team will approach community leaders and local administrative authorities and describe the study to them. Once local leaders and authorities give permission for the study to proceed, they will then inform their communities about the study through public notices, gatherings, and other fora. Thereafter the research team will commence with recruitment of individual study participants.

For recruitment in a selected household, data collectors will introduce themselves and the study, then seek permission to interview from an adult present (18 years and older or according to the local age of majority). The interviewer will follow the steps outlined in the household screening form to first, seek permission to ask screening questions, and then, if permission is granted, determine the number of eligible participants.

If there is an eligible participant, informed oral consent will be obtained before interviewing can commence (see the following section on consent procedure). If he or she is not home but expected back within 30 minutes, the interview team will return to the house no more than three times before finishing all the interviews in the area. If unavailable, he or she will be counted as "Non-response" and will be substituted with someone from another household.

Refer to the country-specific annex for recruitment details.

Consent Process

Members of interview teams, including supervisors and data collectors, will be trained using the JHSPH Human Subjects Research Ethics Field Training Guide. They will also be oriented on the study protocols, data storage procedures, recruitment and consent forms, and data collection tools. Additional training will be provided on interviewing techniques. MCSP Program, Technical, and M&E staff will supervise the interview team during the data collection process. Throughout field-based activities, the data collected will be reviewed daily to identify any potential issues with the interview tools or interviewers. No personal identifiers will be collected, and participants will be assigned study IDs.

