Women and men will provide oral consent to be interviewed. Study participants will be asked individually to consent to being interviewed. Data collectors will explain the purpose of the study, how the household was selected, interview procedures, risks, and benefits. The participants will be informed that they can stop the interview at any time. Emancipated minors (according to local legal definition) who are 15–17 years will provide their own consent as participants. Mothers will provide oral consent for anthropometric measurements to be taken of their children. Adult respondents will be asked to suggest a private location in the homestead or close by where an interview can be conducted in private; all interviews will be conducted at locations that assure audio privacy. Privacy and confidentiality will be maintained during interviews and handling of data obtained. Mothers and fathers with small children may be permitted to participate in the interview in the presence of the child.

We are requesting a waiver of signed consent. The KPC studies will be conducted primarily for the purposes of program learning around integrated service delivery and health systems issues in order to inform national and international programs. A participant's signature on a consent form would, by definition, be a record of the identity of participants. By not having the participant sign or mark a consent form, we can avoid collecting or keeping any identifiers. Study participants will learn about the study and have ample chance to ask questions about the study through use of the enrollment and consent script.

Study Implementation

- 1. Participants will be recruited (approximately 5 minutes) and consent will be obtained (approximately 5 minutes) and then the questionnaire will be administered.
- 2. Each household will be visited no more than three times in an attempt to locate a selected respondent. The interview will take about 60–75 minutes depending on the number of modules included for that country. Interviews will take place in or near the home, in a private location where the interview is unlikely to be overheard.

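### Call-backs are provided only for absent respondents due back within 30 minutes; those away longer are replaced, which is likely to under-represent parents out in the daytime

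*Protocol*

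**What the plan says.** The rule for absent respondents stands in section 3, Respondent Selection (within a Household). If the eligible person is "not home but expected back within 30 minutes, the interview team will return to the house no more than three times", the window for those returns runs until the team has finished interviewing in the area. Someone who is unavailable is recorded as non-response and "substituted with someone from another household". The next paragraph adds: "When no eligible mother or father is available in a household, then the interview team proceeds to the next house selected to be visited". The section also says of the household screening record: "The screening form will be destroyed at the end of the fieldwork".

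Section 4, Recruitment Process, repeats the call-back rule with the same 30-minute condition and ends: "Refer to the country-specific annex for recruitment details".

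Section 4, Study Implementation, item 2, gives a visit rule without that condition: "Each household will be visited no more than three times in an attempt to locate a selected respondent".

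Sample Size Determination sets 95% confidence and 10-point precision for key indicators. On fieldwork volume it says: "The number of households visited will be calculated based on estimates of the percentage of families expected to have children in the needed age groups".

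**The concern.** Return visits are triggered by a short expected absence. For a parent at work, in the field or at market for half a day, the generic protocol provides substitution but no call-back. Inclusion then depends on being at or near home when the team arrives. Being home in the daytime plausibly goes with sex, employment and distance to services, and these plausibly go with knowledge, care seeking and coverage, which the survey is meant to measure. Fathers and men can be chosen as respondent groups, fathers appear with their own denominator in the parallel-sampling table, and interviews take place in or near the home, so the loss probably falls hardest on them.

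Substitution keeps the number of completed interviews at target. The confidence interval therefore has its planned width while the sample leans towards people easily found at home, and a larger sample would not cure that. Surveys are repeated to measure change, so a shift in daytime absence between rounds could be read as programme effect.

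**Working it through.** **1. The three statements of the rule, side by side**

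| Section | Condition for a return | Limit |
|---|---|---|
| Respondent Selection | due back within 30 minutes | at most three returns |
| Recruitment Process | due back within 30 minutes | at most three returns |
| Study Implementation, item 2 | none stated | at most three visits per household |

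All three set a maximum and none sets a minimum. The third can be read as a ceiling that leaves the 30-minute condition in force, or as permission to revisit any selected respondent. A field team cannot tell which. The counts also differ if taken literally: a first call plus three returns is 1 + 3 = 4 visits, against three in all.

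**2. The plan's own figures**

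- Single survey: N = 1.96² × 0.5 × 0.5 / 0.10² = 96.04, stated as 96. With a design effect of 2: 192. Both reproduce.
- Households to visit: 166 × 100/45 = 368.9, stated as 369; and 262 × 100/45 = 582.2, stated as 582. Both reproduce. The only divisor is the share of eligible households.

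**3. Bias from replacement**

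Let *a* be the share of eligible respondents who are away too long and are replaced, and *D* the indicator among those available minus the indicator among those absent. If replacements resemble those available, the survey estimates p(available), while the target is (1 − a) × p(available) + a × p(absent). Hence

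bias = a × D.

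The documents give neither *a* nor *D*. Both are assumptions here: *a* from 10% to 40%, *D* from 10 to 30 points.

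**4. Effect on the nominal 95% interval**

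With p = 0.5 and N = 96, SE = √(0.25/96) = 0.0510. The 30-cluster case gives the same SE, since √(2 × 0.25/192) = √(0.25/96). True coverage is Φ(1.96 − bias/SE) − Φ(−1.96 − bias/SE). Each cell shows bias in points, then true coverage:

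| a | D = 10 | D = 20 | D = 30 |
|---|---|---|---|
| 10% | 1; 94.6% | 2; 93.2% | 3; 91.0% |
| 20% | 2; 93.2% | 4; 87.7% | 6; 78.3% |
| 30% | 3; 91.0% | 6; 78.3% | 9; 57.8% |
| 40% | 4; 87.7% | 8; 65.2% | 12; 34.8% |

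**5. Effect on measured change**

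The bias in a difference between rounds is a₂D₂ − a₁D₁. It is zero if both quantities are stable. If, on assumed values, *D* stays at 20 points and *a* moves from 10% to 30%, the spurious change is 6 − 2 = 4 points.

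**The case against.** The strongest reply is that the rule is conditional and not a prohibition. The text says what to do for a short absence and is silent on a longer one. A reader might infer that longer absentees are barred from any return visit, or replaced on the spot. The documents do not say so: the clause on unavailability carries no timing, and item 2 of Study Implementation may allow more. What stands is narrower. No call-back is provided, substitution is, and the sections do not agree.

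Second, recruitment details are deferred to country annexes. That is true, but nothing requires an annex to add call-backs, so the 30-minute rule remains the default.

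Third, the size is wholly assumed. The lower part of the range is well inside the ±10-point target, and fathers and men are optional groups. This stands, and it is why no figure for the bias can be asserted.

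Fourth, a reader might infer that the household calculation is wrong because it has no non-response term, or that substitution should be forbidden. Neither follows. Under the present rule substitution fills the target, so no allowance is needed to reach the count, and visiting more households would leave the bias untouched. A ban would make the achieved count random, which conflicts with the LQAS minimum of 19 interviews per supervision area. It also fits poorly with spin-the-bottle and mapping, where households are picked in sequence in the field. Nor is the loss wholly hidden, since unavailable people are to be counted as non-response.

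Finally, the survey is meant to be rapid and cheap, so some limit on call-backs is a legitimate trade-off. That supports a cap on visits, which the protocol already has, more than a 30-minute entry condition.

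**Conclusion.** The point holds as a weakness of the default field procedure together with an inconsistency between sections. Two sections make call-backs depend on a return within 30 minutes and provide only substitution for longer absences; a third states a visit ceiling without that condition. Followed as written, this is likely to under-represent parents away in the daytime, fathers and men most of all, while the interview count and nominal precision appear intact.

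The direction is an inference from the procedure; the documents say nothing about working status. The size cannot be taken from them. With 10–40% replaced and a 10–30 point difference, both assumed, the bias is about 1–12 points. The case of 20% and 20 points gives 4 points and 87.7% true coverage. A reader might go further and conclude that every indicator, or every measured trend, is materially biased. That is not supported: at the low end the effect is negligible, and change is affected only if absence, or the way absent people differ, shifts between rounds. The change is worth making because it is cheap and a larger sample cannot replace it.

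**What to change.** Delete the 30-minute condition in Respondent Selection and in Recruitment Process. Any selected respondent who is out, but whom the household expects back before the team finishes the area, is then revisited within the existing maximum of three visits. Align Study Implementation, item 2, with that text, and state whether the three include the first call. Keep substitution, but only after those call-backs. Tally non-response by sex and respondent group before the screening forms are destroyed, and report it with each survey's results.

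The cost is some revisit or waiting time. It is small in 30-cluster surveys, where the team stays for 7–30 interviews per cluster. It is larger under LQAS (at least 95 clusters, 19 × 5) and stratified sampling (at least 96 clusters for N = 96), where there may be about one interview per cluster and waiting means waiting in each place. The target number of interviews does not change.
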